**Metabolic Analysis for Treatment Choice in Gestational Diabetes Mellitus
(MATCh-GDM)**

Magee Womens' Hospital of UPMC

Department of Obstetrics, Gynecology and Reproductive Sciences

March 1, 2018
NCT# 03029702

PI: [name]
E-mail: [contact]

I. Abstract:

Gestational diabetes (GDM) is a significant clinical and public health burden, affecting over 400,000 pregnant women in the United States each year. Without adequate treatment, women with GDM and their infants are at risk for substantial morbidity. Because of this, experts recommend treatment focused on normalization of hyperglycemia to improve outcomes. However, providers have limited capacity to predict which treatment will achieve glycemic goals. This results in a choice based on provider and patient preference and a trial and error approach, which can create delays in glycemic control within the short (8-10 weeks) window between diagnosis and delivery. Maternal and fetal morbidity may be related to a mismatch between glycemic pathophysiology and the mechanism of action of glucose lowering agents. In fact, GDM is heterogeneous, with predominant insulin resistance (IR) in 50%, insulin secretion deficit (ISD) in 30%, and a combination of both in 20% of women as underlying mechanisms of hyperglycemia. This variation in GDM pathophysiology and clinical outcomes supports the use of an individualized treatment approach. The overall goal of this project is to investigate an individualized treatment approach for GDM where treatment is based on each woman's GDM mechanism.

II. OBJECTIVES

The overall objective is to perform a pilot study using an individualized treatment approach for GDM where treatment is based on each woman's GDM mechanism.

Aim 1: Evaluate the feasibility of conducting a pilot RCT comparing individualized GDM treatment and usual care (treatment chosen by provider and patient without regard for pathophysiologic heterogeneity).

Sixty pregnant women with GDM will be randomized to individualized treatment based on GDM mechanism (determined at the time of a 3-hour oral glucose tolerance test (OGTT) vs. usual care. We will measure feasibility by the proportion of women who are eligible, who enroll, and who remain in the study.

Aim 2: Inform the design of a larger RCT comparing individualized GDM treatment and usual care.

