We will assess the consistency of the GDM causal mechanisms with a repeat OGTT two weeks after treatment initiation, adherence to treatment assignment and dose titration, and the distribution of adipose-related metabolism covariates (e.g. obesity, lipid profile, free fatty acids). This data will be used to inform the study design, data collection procedures and outcomes measures of the large-scale RCT.

Aim 3. Assess participant and provider acceptability of an RCT comparing individualized GDM treatment and usual care.

We will conduct individual semi-structured interviews with 3 groups: (1) pilot participants (n=16), to determine acceptability and burden of the study; 2) prenatal care providers (n=15) to determine their satisfaction with study procedures, and 3) women who are approached but decline to participate in the pilot study (n=15) to determine barriers to participation.

III. PARTICIPANTS

Inclusion criteria:

Pregnant women 18-45 years old, beyond 24 weeks of gestation, who are scheduled for a 3-hour oral glucose tolerance test.

Exclusion criteria:

- Preexisting type 1 or type 2 DM
- Multiple gestation
- GDM diagnosis without 3-hour OGTT
- Oral or IV corticosteroid use in the past 7 days
- Major congenital anomaly with anticipated preterm delivery
- Allergy to glyburide, metformin or sulfa
- History of severe pulmonary disease(pulmonary requirement for oxygen therapy or daily treatment for restrictive or obstructive pulmonary disease)
- History of hepatic disease (LFT's greater than two times of upper normal range)
- History of renal disease (serum creatinine higher than 1.2 mg/dL)
- History of heart failure or myocardial infarction

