IV. Outcome Measures- The primary objective of the pilot study is to evaluate the feasibility of conducting a randomized trial comparing individualized treatment versus usual care for GDM. Our primary feasibility outcomes will be the number (proportion) of women who are eligible, screened, enrolled and remain in the study at each outcome assessment. As pregnant women are a difficult population to retain, we will identify any issues related to recruitment, enrollment and retention that will be necessary to account for when determining the sample size estimated for the future trial. Reasons for exclusion and subject refusal will be tracked at the time of screening by the research team. We will assess reasons for participant attrition through a follow-up call or e-mail at the time of withdrawal. We will determine the proportion of women who remain on the treatment assigned at the beginning of the pilot within each arm. We will review health records to determine the reason for changing treatments. We will measure trough levels at the time of the repeat OGTT. We will also review treatment titration to assess the proportion of participants who are titrated according to the protocol.

V. Analysis Plan – Demographic characteristics, such as race, age, parity, and insurance will be compared between study arms to assess balance and comparability. Descriptive summaries will include the mean and standard deviations (or medians and quartiles for skewed distributions) for continuous variables and frequencies and proportions for categorical variables. Due to the pilot nature of this RCT, hypothesis testing is not the primary focus, but rather estimation within each study arm.

VI. Sample Size - We will introduce the pilot trial to all women undergoing an OGTT. We plan on screening 300 women to allow us to include ~60 women in the pilot study. This sample size

will allow us to have various GDM mechanisms represented. Assuming 30 women within each study arm and a 5% type I error rate, we will have the ability to estimate within-arm 95% confidence interval margin-of-errors of no more than 0.18 for each of our feasibility outcomes.

VII. Study Procedures:

Screening Visit

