- Fill a pre-prepared red top tube with 4 mL of blood (insulin, c-peptide, free fatty acids)
 1. Gently invert tube five times to avoid clotting
 2. Place sample on ice
 3. Centrifuge sample at 1200 RFG (approximately 3000rpm) at 4°C for 15 minutes

[figure not shown]
Sample processing:

1. Materials and equipment needed per participant

a. During study visit:

- 1.5mL cryovials (**fill each with 1mL**)
- Labels for cryovials which should include subject ID, visit number and sample time following the study's protocol. Please indicate light green (LG) or red (R) on the cryovials to help differentiate samples

Cryovial Label appearance

The blood specimens will be processed at the CTRC and vials will be transferred **WEEKLY** to the central lab for analysis as per Table 2. All remaining vials will be stored at the CTRC at least at -70.

Table 2. Number of microvials to be transferred to the central lab for analysis

Time Intervals (in mins)	Insulin; C-peptide, free fatty acids,	Lipids
Microvial	Red	Green
0	2	1
60	2	
120	2	
180	2	

Women who are diagnosed with gestational diabetes are eligible for the pilot study.

Study visit #1

Each woman will meet with a physician from the study team and be randomized to one of two study treatment groups: individualized therapy or usual care. A randomization sequence will be generated and incorporated into the database prior to recruitment. Permuted block randomization with randomly varying block sizes will be performed by a web-based data entry system.

All women diagnosed with GDM will be started with medical nutritional therapy as per clinical guidelines. The decision to start treatment is based on home glucose values after 1-2 weeks of medical nutritional therapy. Pharmacologic treatment is recommended if fasting values are greater than 95mg/dl or postprandial values are greater than 140mg/dL. Initiation of usual care vs/ individualized treatment will only occur once glucose values exceed these goals despite medical nutritional therapy. Following initiation of pharmacologic therapy, and throughout gestation, home blood glucose levels will be reviewed weekly and the doses of drugs will be adjusted in person during a clinic visit or via telephone per the email.

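### The 0.18 margin needs all 30 women per arm, so it is not guaranteed for outcomes that exist only once a drug is started: repeat-OGTT attendance and, if covered, adherence and titration

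*Combined protocol and SAP*

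**What the plan says.** The end of the screening part of VII. Study Procedures sets one condition for entering the pilot: "Women who are diagnosed with gestational diabetes are eligible for the pilot study". Aim 1 in II. Objectives agrees: "Sixty pregnant women with GDM will be randomized to individualized treatment based on GDM mechanism". Neither requires that a woman need a drug.

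Under Study visit #1, each woman meets a study physician and is randomised. The text then puts every woman on nutritional therapy and bases the drug decision on home glucose readings after 1-2 weeks. A drug is recommended if fasting values are above 95 mg/dL or postprandial values above 140 mg/dL. It adds: "Initiation of usual care vs/ individualized treatment will only occur once glucose values exceed these goals despite medical nutritional therapy". Study visit #3, the repeat OGTT, falls two weeks after treatment begins.

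IV. Outcome Measures names as primary feasibility outcomes the number and proportion of "women who are eligible, screened, enrolled and remain in the study at each outcome assessment". The same section then says: "We will determine the proportion of women who remain on the treatment assigned at the beginning of the pilot within each arm". It also plans a review of dosing to "assess the proportion of participants who are titrated according to the protocol". II. Objectives lists "adherence to treatment assignment and dose titration" under Aim 2.

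VI. Sample Size assumes 30 women per arm and promises within-arm 95% "margin-of-errors of no more than 0.18 for each of our feasibility outcomes". No section states how many randomised women are expected to start a drug, or the denominator for visit #3 attendance, adherence or titration.

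**The concern.** A woman whose glucose is controlled on nutritional therapy has no date for visit #3, no assigned drug to stay on and no dose to titrate. She can still be followed through prenatal visits and delivery, so she counts fully for enrolment and overall retention. Two kinds of outcome are therefore covered by one margin: those measurable in everyone randomised, and those measurable only in women who start a drug.

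The pilot exists to estimate these proportions and to feed them into the planning of a larger trial. If the second kind rests on fewer than 30 per arm, the stated ceiling may not be met. If diet-controlled women are instead left in the denominator, the estimate mixes women who needed no drug with women who did not attend or did not adhere.

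**Working it through.** **Inputs.** From VI. Sample Size: 30 per arm, 95% confidence, margin at most 0.18, about 60 women included from 300 screened. The share of randomised women who start a drug is not in the documents; 90%, 80% and 60% are assumptions chosen to show a range.

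**Formula.** Margin = 1.96 × √(p(1−p)/n), largest at p = 0.5.

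**The plan's own figure.** At n = 30 and p = 0.5: 1.96 × √(0.25/30) = 0.179, which matches 0.18. The smallest n that satisfies 0.18 is (1.96 × 0.5/0.18)² = 29.6, so 30. At n = 29 the margin is 0.182. There is no slack.

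**With starters only.** Starters per arm = 30 × share. The fourth column is the smallest proportion above 0.5 that keeps the margin within 0.18, from 0.5 + √(0.25 − n(0.18/1.96)²), rounded up.

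| Share starting (assumed) | Starters per arm | Margin at p = 0.5 | Proportion needed for 0.18 | Margin at p = 0.7 | Margin at p = 0.9 |
|---|---|---|---|---|---|
| 90% | 27 | 0.189 | 0.65 | 0.173 | 0.113 |
| 80% | 24 | 0.200 | 0.72 | 0.183 | 0.120 |
| 60% | 18 | 0.231 | 0.82 | 0.212 | 0.139 |

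The ceiling is exceeded in the worst case at every share. At a true proportion of 0.9 the margin is within 0.18 throughout. At 0.7 it exceeds 0.18 when the share starting is 80% or 60%.

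**Interval method.** The plan does not name one. The formula above is the one that reproduces 0.18. Near p = 0.5, the Wilson half-width is 0.169 at n = 30, 0.176 at 27 and 0.186 at 24. The Clopper-Pearson half-width is 0.187 already at n = 30.

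**Keeping all 30 in the denominator.** Suppose 90% of starters stay on their drug (assumed).

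- 80% start: adherence is 0.90 among starters, 0.80 × 0.90 = 0.72 if diet-controlled women count as not on treatment, and 0.72 + 0.20 = 0.92 if they count as adherent.
- 60% start: the three figures are 0.90, 0.54 and 0.94.

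The choice of denominator alone shifts the estimate by 0.20 (0.92 − 0.72) or 0.40 (0.94 − 0.54), more than the margin being promised.

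**The case against.** The order of events is inferred. Visit #1 is undated, and the text under it also covers prescribing, with no exception for women controlled on diet. If visit #1 in practice follows failure of nutritional therapy, the problem disappears. The planned yield of about 60 from 300 may also already allow for such women. This stands as a limit. Even so, eligibility rests on diagnosis alone, the sentence about initiation conditions the start of treatment and not randomisation, and the adherence outcome speaks of treatment assigned at the beginning of the pilot.

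Coverage can also be disputed. Remaining in the study may mean only not having withdrawn, which keeps 30 in the retention denominator. Adherence and titration are Aim 2 items, and in IV. Outcome Measures they fall outside the sentence naming the primary feasibility outcomes. Both points are fair. However, retention is to be assessed at each outcome assessment, and the repeat OGTT is one of them. The sample size sentence makes no exceptions.

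Three stronger readings are tempting, and the documents do not support them.

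- A reader might infer that the whole precision statement fails. It does not: enrolment and retention through delivery use all 30 per arm. The 8 interviews per arm planned at the second OGTT would be met even with 18 starters.
- A reader might infer that a known allocation biases who starts a drug. No blinding of that decision is described, so it is possible. But the numerical trigger is the same in both arms, nothing shows a differential incentive, and hypothesis testing is not the main aim.
- A reader might infer that randomising later would restore 0.18. From the same 300 screened it yields the same number of starters, and so the same margins.

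**Conclusion.** The point holds in a limited form. On the most natural reading of visit #1, and with the formula that reproduces the plan's figure, 0.18 is guaranteed only for outcomes measured on all 30 women per arm. For repeat-OGTT attendance it is not guaranteed once any woman in an arm is controlled on nutritional therapy. The same applies to adherence and titration if the 0.18 is meant to include them. At assumed start shares of 90%, 80% and 60% the worst-case margin exceeds the stated 0.18 by 0.009, 0.020 and 0.051.

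These are worst cases at p = 0.5, and high attendance or adherence would bring the achieved margin back within 0.18. The more practical defect is the unstated denominator, because it changes what the reported proportion means. Confidence is medium, because the timing of visit #1 and the scope of the 0.18 are both readings of the text.

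**What to change.** **Change to make.**

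- State when visit #1 takes place relative to the 1-2 weeks of nutritional therapy.
- Define women who started a drug as the denominator for repeat-OGTT attendance, adherence and titration, and report the number starting in each arm.
- Limit the 0.18 to outcomes measured on all 30 per arm.
- Give the expected number of starters and the margin that goes with it.

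This costs a few sentences and no extra women.

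**Optional design change.** Keep consent and sampling at the screening OGTT and start nutritional therapy for all. Randomise when the protocol's own glucose criterion for a drug is met, before a drug is chosen. Starting is then judged before allocation is known, and every randomised woman is due at visit #3.

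The cost is that randomisation comes 1-2 weeks later. If the planned yield does not already allow for diet-controlled women, 300 screened would give 60 × share = 54, 48 or 36 randomised at the three assumed shares. The smaller arms would then also apply to retention at delivery. On the same condition, reaching 60 starters would need 300/share, or about 333, 375 or 500 screened. The option therefore makes the denominators clean but does not by itself restore 0.18.

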Time Intervals (in mins)	Glucose	Insulin; C-peptide, free fatty acids,	Lipids
Microvial	Grey	Red	Green
0	1	2	1
60	1	2	
120	1	2	
180	1	2	

Interviews will occur at the time of the second OGTT for women who are enrolled in the study and at the time of refusal for those who opt out. Interviews will focus on participant/provider perception of study/treatment and whether they experienced any burdens. 16 participants (8 in each group) will be interviewed along with 10 women who decline to enroll in the study but agree to an interview.

Additional study visits:

During a participant's routine prenatal visits (which typically occur every 1-2 weeks) with her provider that occur between 29 and 40 weeks of gestation, she will also meet with a member of the research team who will record information about her blood glucose measurements, pregnancy, weight, and any side effects she had since the last study visit. These study visits will occur in her provider's office and will take no more than 10 minutes to complete.

At the time of labor and delivery

Delivery: At delivery, the hospital research nursing team we will measure infant birth weight and length at delivery. We will collect umbilical cord venous blood for assay of c-peptide. We will only collect these samples if it is safe to do so and possible to do so based on staffing.

Air displacement plethysmography will be used to measure body composition (PEA POD; Life Measurement Inc, Concord, CA) in the newborns within 72 hours post-delivery to provide an estimate of percent body fat and lean body mass.

Data abstraction: Once written consent is provided and participant completes the first study visit, a member of the research team will conduct at least two prenatal and two postnatal EHR data abstraction from the prenatal and delivery records: type of delivery, prenatal and delivery complications. We will also collect information regarding any treatment for gestational diabetes as well as the number of ultrasounds and tests for assessment of fetal well-being (biophysical profiles, non-stress tests).

VIII. Participant withdrawal:

Participants may withdraw from the study at any time.

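### Aim 3 participant interviews are scheduled only at the repeat OGTT, so women who leave before it, or who never start drug treatment, have no interview and burden is likely to be understated

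*Combined protocol and SAP*

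**What the plan says.** Section II, Aim 3, sets up the interviews: "We will conduct individual semi-structured interviews with 3 groups: (1) pilot participants (n=16), to determine acceptability and burden of the study". The second group is "prenatal care providers (n=15) to determine their satisfaction with study procedures". The third is "women who are approached but decline to participate in the pilot study (n=15) to determine barriers to participation".

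The timing is in Section VII, after the study visit #3 procedures: "Interviews will occur at the time of the second OGTT for women who are enrolled in the study and at the time of refusal". The refusal time applies to women opting out, whom the same paragraph identifies: "16 participants (8 in each group) will be interviewed along with 10 women who decline to enroll in the study but agree to an interview". (Aim 3 gives 15 decliners and Section VII gives 10. That is a separate inconsistency to reconcile and does not affect this point.)

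Section VII places randomization at study visit #1. Nutritional therapy comes first, and study treatment starts only if home glucose values exceed the stated goals after 1-2 weeks of it. Study visit #3 is a fasting visit of about 3-4 hours, dated from the start of treatment. Section VIII lets women withdraw at any time.

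Section IV anticipates attrition: "As pregnant women are a difficult population to retain, we will identify any issues related to recruitment, enrollment and retention". It also plans a contact with women who leave: "We will assess reasons for participant attrition through a follow-up call or e-mail at the time of withdrawal".

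**The concern.** Aim 3 asks how acceptable and burdensome the study is to pilot participants. Under the timing rule, a woman can answer only if she began study treatment, stayed two more weeks and came to a long fasting visit. One who left because of her assignment, her drug or the prospect of a second 3-hour test is not interviewed as a participant, and having enrolled she is not a decliner. Being interviewed thus depends partly on the quality being measured.

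A second group is missed for a different reason. Women controlled on nutritional therapy remain in the study, but no treatment start fixes the date of their second OGTT.

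What is at stake is the use of Aim 3 in planning the larger trial. The protocol expects retention to be difficult, and early leavers are well placed to describe the burdens that lead women to leave. Interviews with stayers alone can miss those themes.

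**Working it through.** **The plan's own figure.** There is none for the interviews. The only precision statement, in Section VI, concerns the feasibility proportions. It reproduces: 1.96 × √(0.25/30) = 0.179, against the stated 0.18. Nothing below depends on it.

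**Who has an interview time.** Setting Section II (Aim 3) beside Section VII:

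| Group | Interview time in the plan |
|---|---|
| Approached, declines to enrol | At refusal |
| Enrolled, starts treatment, attends visit #3 | At the second OGTT |
| Enrolled, withdraws or stops attending before visit #3 | None |
| Enrolled, controlled on nutritional therapy alone | None, because visit #3 is dated from treatment initiation |

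The last row assumes that randomization precedes the nutritional therapy period, as the order of text under study visit #1 indicates. If randomization came after that period, the last row would be empty and the third would stand.

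**Time at risk before the interview.** 1-2 weeks of nutritional therapy plus 2 weeks of treatment gives at least 3-4 weeks from the start of nutritional therapy.

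**How many leavers a representative sample would hold.** The inputs from the documents are 60 women (Section VI) and 16 interviews (Aim 3). The attrition *d* before visit #3 is assumed, because the plan gives no rate. With L = 60*d* leavers and 16 drawn at random from 60, the expected number is 16L/60, and the chance of at least one is 1 − C(60−L, 16)/C(60, 16).

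| *d* (assumed) | L | Expected leavers in 16 | Chance of at least one | Under the written rule |
|---|---|---|---|---|
| 10% | 6 | 1.6 | 0.859 | 0 |
| 20% | 12 | 3.2 | 0.985 | 0 |
| 30% | 18 | 4.8 | 0.999 | 0 |

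The plan does not say that the 16 are drawn at random. The random draw is only a benchmark for a representative sample.

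**Direction of the effect, as illustration only.** Let *s* and *l* be the shares of stayers and leavers who feel a serious burden. The share in all women is (1−*d*)*s* + *dl*, and stayers alone show *s*. Take *s* = 0.20 and *l* = 0.60 or 0.80, both assumed:

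- *d* = 10%: 0.18 + 0.06 = 0.24, or 0.18 + 0.08 = 0.26. Stayers show 0.20, which is low by 0.04/0.24 = 17% or 0.06/0.26 = 23%.
- *d* = 20%: 0.16 + 0.12 = 0.28, or 0.16 + 0.16 = 0.32. Stayers show 0.20, which is low by 0.08/0.28 = 29% or 0.12/0.32 = 38%.

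These percentages follow from setting leavers' burden at three to four times that of stayers. The plan does not propose to estimate a burden percentage from the interviews, so they show direction and nothing firmer.

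**The case against.** The strongest reply is that the plan already hears from women who leave. Section IV counts who remains at each outcome assessment, asks about reasons for attrition at withdrawal, and reviews health records for reasons for changing treatment. A woman who leaves over her drug or the second OGTT can say so. This stands as mitigation, and it means that the retention outcomes are not compromised. It does not close the gap: the contact may be only an e-mail, it is not tied to Aim 3, and it does not mention acceptability or burden.

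The visit #3 timing also has a rationale. By then a woman has experienced two weeks of treatment and is at the repeat test, which an early leaver has not experienced. That supports visit #3 as the main interview time, but not as the only one.

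Several stronger readings are tempting, and the documents do not support them:

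- *That Aim 3 as a whole hears only from women who tolerated the study.* Providers and decliners are interviewed too. The point concerns the participant interviews.
- *That leavers are expressly excluded.* Section VII states a time, not an exclusion. The gap is inferred from the timing.
- *That everyone missed is dissatisfied.* Women controlled on nutritional therapy are still in the study, and Section IX's preceding withdrawal rules (Section VIII) also allow removal for unscheduled eating or for meeting an exclusion criterion.
- *That an eight-versus-eight comparison of acceptability is biased.* No such comparison is planned. Section VII gives only the number per group, and Section V puts estimation within each arm ahead of testing.

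**Conclusion.** The point holds for the participant interviews. As written, they cover only women who started treatment and stayed to visit #3, and so are likely to understate burden among all enrolled women. That direction assumes that early leavers found the study more burdensome, on average, than those who stayed. This is plausible but not shown in the documents.

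The certain part of the size is that the stated timing yields no interviews with women who left before visit #3. The comparison with about 2 to 5 in a representative 16 rests on the assumed 10-30% attrition. The number of women controlled on nutritional therapy cannot be estimated from the documents.

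The consequence is limited to one qualitative aim of a pilot, and the Section IV contact softens it. The change is still worth making, because it is cheap and these interviews are meant to inform the larger trial.

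**What to change.** Replace the timing sentence for enrolled women in Section VII with: *Enrolled women will be interviewed at the second OGTT or, if they withdraw or stop attending before it, at the follow-up contact in Section IV (by telephone if they agree); women who remain on nutritional therapy alone will be interviewed at a routine study visit.*

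Keep 16 places, 8 per arm, and fill them purposively as recruitment proceeds. Include early leavers as they occur, up to about 2 per arm. Holding places back and releasing them later would work badly, because attenders pass visit #3 before later withdrawals are known. Report leavers separately from women who attended visit #3. If few leavers agree, state that the findings apply to women who reached visit #3.

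The cost is a short amendment and some interviewer time by telephone; the total number of interviews does not change. With 2 leavers per arm, 8 − 2 = 6 places per arm remain for visit #3 attenders and women on nutritional therapy alone, so somewhat fewer attenders are interviewed. Some leavers will refuse.

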- Fill a pre-prepared red top tube with 4 mL of blood (insulin, c-peptide, free fatty acids)
 1. Gently invert tube five times to avoid clotting
 2. Place sample on ice
 3. Centrifuge sample at 1200 RFG (approximately 3000rpm) at 4°C for 15 minutes
- Fill a pre-prepared light green top tube with 4 mL of blood (lipids)
 1. Gently invert tube five times to avoid clotting
 2. Place sample on ice
 3. Centrifuge sample at 1200 RFG (approximately 3000rpm) at 4°C for 15 minutes

b. At times **60, 120 and 180** (glucose, c-peptide, and insulin)

- Fill a grey top tube with 4mL of blood (glucose)
 1. Gently invert tube 5 times to avoid clotting
 2. Place sample on ice
 3. Centrifuge sample at 1200 RFG (approximately 3000rpm) at 4°C for 15 minutes
- Fill a pre-prepared red top tube with 4 mL of blood (insulin, c-peptide, free fatty acids)
 1. Gently invert tube five times to avoid clotting
 2. Place sample on ice
 3. Centrifuge sample at 1200 RFG (approximately 3000rpm) at 4°C for 15 minutes

Sample processing:

2. Materials and equipment needed per participant

a. During study visit:

- 1.5mL cryovials (fill each with 1mL)

- Labels for cryovials which should include subject ID, visit number and sample time following the study's protocol. Please indicate light green (LG), red (R), or grey (G) on the cryovials to help differentiate samples

Cryovial Label appearance

[name] MATCH-GDM
Visit#
Subject (ID)
Sample time LG/R/G

Notes:

- If blood draw exceeds indicated volume, please add any excess volume of blood to red top tubes and process the sample according to protocol.**
- Protocol allows for a volume up to 1ml of discarded blood for each blood draw**

C. Questionnaires: participants will complete a demographic sheet, and brief questionnaires assessing lifestyle factors such as physical activity, sleep quality and diet.

D. Height and weight will be measured using standard protocols. Maximum hip circumference and skinfold thickness over biceps, triceps, subscapular and supra iliac regions will be measured using previously published methods.

E. Once the OGTT is completed, the CTRC staff will assess for any problems with the testing and the participant will be discharged

F. The blood specimens will be processed at the CTRC and vials will be transferred to the central lab for analysis as per Table 4. All remaining vials will be stored at the CTRC at least at -70.

Table 4. Number of microvials to be transferred to the central lab for analysis

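### No systematic side-effect record is specified before 29 weeks, and the look-back wording can omit the first two weeks of drug treatment for women who start before about 27 weeks

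*Combined protocol and SAP*

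**What the plan says.** The one instruction to record drug side effects is in section VII, Additional study visits. It concerns prenatal visits "that occur between 29 and 40 weeks of gestation", at which research staff note, among other things, "any side effects she had since the last study visit".

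The other relevant provisions are:

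- **Entry (section III):** "Pregnant women 18-45 years old, beyond 24 weeks of gestation, who are scheduled for a 3-hour oral glucose tolerance test".
- **Drug start (section VII, Study visit #1):** "The decision to start treatment is based on home glucose values after 1-2 weeks of medical nutritional therapy". From drug start, home glucose is reviewed weekly and doses are adjusted. Side effects are not mentioned there.
- **Study visit #2:** a hemoglobin check if none is recent, with no stated timing and no side-effect item.
- **Study visit #3:** a repeat OGTT two weeks into drug treatment, with demographic and lifestyle questionnaires. Afterwards "the CTRC staff will assess for any problems with the testing", which concerns the OGTT and not the drug.
- **Interviews (section VII):** 16 participants, 8 per arm, are asked at the second OGTT how they perceive the treatment and what burdens they met.
- **Records (sections IV and VII):** health records are reviewed for why treatment was changed, and complications are abstracted from the EHR.

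**The concern.** The 29-week opening of the side-effect window does not fit the plan's own entry limit and treatment timing. A woman can be on a drug, and through her first dose adjustments, before the window opens. The look-back rule may not recover that period, because visit #3 can fall between drug start and the first contact.

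The protocol expects drug side effects: section VII (Study visit #1) has women take the medication with food to lessen them. Section VIII stops the study if risks come to outweigh benefits, a judgement that needs side-effect data from the start of exposure. Aim 2 uses the pilot to settle data collection procedures for a larger trial, so a gap left here could be carried forward.

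**Working it through.** **The plan's statistical figure.** Section VI gives a within-arm 95% margin of error of at most 0.18 with 30 women per arm. It reproduces: 1.96 × √(0.5 × 0.5 / 30) = 0.179. This point does not depend on it or change it. The check below is a timeline.

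**Inputs**

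- g, week of the screening OGTT: from 24 (section III).
- m, nutritional therapy before a drug: 1-2 weeks (section VII, Study visit #1).
- L, lag from OGTT to randomization: not given; assumed 0-1 week.
- Visit #3: drug start + 2 weeks (section VII, Study visit #3).
- Side-effect contacts open at 29 weeks (section VII, Additional study visits).

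**Formulas**

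- Drug start s = g + L + m
- Visit #3 = s + 2
- Shortest wait from first dose to a side-effect contact = max(0, 29 − s)

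**Results**

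| g | L | m | Drug start | Visit #3 | Wait (weeks) | First two weeks on drug, taking visit #3 as the last study visit |
|---|---|---|---|---|---|---|
| 24 | 0 | 1 | 25 | 27 | 4 | Outside the look-back |
| 24 | 0 | 2 | 26 | 28 | 3 | Outside the look-back |
| 24 | 1 | 2 | 27 | 29 | 2 | Depends on which contact comes first |
| 26 | 0 | 2 | 28 | 30 | 1 | First contact can precede visit #3; depends on order |
| 27 | 0 | 2 | 29 | 31 | 0 | Contacts already running |

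The waits are minimums. The contacts ride on "routine prenatal visits (which typically occur every 1-2 weeks" apart, so the first may come up to about two weeks after the window opens. In the first two rows the weeks from visit #3 onward are covered by the look-back. What is lost is the two weeks between first dose and visit #3.

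**How many women?** The documents give no distribution of gestational age at the OGTT, so the share cannot be computed. The Abstract gives a window of 8-10 weeks from diagnosis to delivery. Assuming delivery at 38-40 weeks:

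- Diagnosis: 38 − 10 = 28 to 40 − 8 = 32 weeks.
- Drug start: 28 + 1 = 29 to 32 + 2 = 34 weeks.

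With delivery at 37 weeks the earliest start is 37 − 10 + 1 = 28. A start before 27 weeks needs diagnosis before 26 weeks (27 − 1). Under the quoted window that means delivery before 36 weeks (26 + 10). The affected women therefore sit at the early edge of eligibility.

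**Other capture.** The interviews reach 16/60 = 27% of participants.

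**The case against.** The strongest reply concerns the look-back. Section VII numbers visits #1 to #3 as study visits, but it also calls the recurring prenatal contacts study visits. If the phrase means the previous contact at which this information was recorded, the first contact at 29 weeks can reach back over all treatment so far. That reading is possible, so the two-week omission is a consequence of the literal wording and not a certainty. Two things survive it: the text lets staff apply either reading, and on the generous one an early starter is still first asked 3-4 weeks or more after her first dose.

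A reader might infer that early side effects are never asked about at all. The documents do not support that. The interviews fall two weeks into treatment, section VIII has staff elicit how comfortable the woman is at the study visit, and record abstraction has no 29-week lower limit. None of these is a systematic side-effect record: the interviews reach about a quarter of the women, the comfort check sits among the precautions for fasting and the test day, and abstraction is passive.

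A reader might also infer bias between arms, or in the reasons for changing treatment. Neither is shown. The recording schedule is the same in both arms, all three drugs can be used in either, side effects are not among the section IV outcomes, and section V plans estimation within arms. Reasons for changing treatment come from health records, which the 29-week window does not restrict.

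Nor can a failure of safety oversight be concluded. Treated women have weekly glucose review from drug start, and the Appendix A figures are not visible, so what they say about tolerability cannot be judged.

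**Conclusion.** The point holds in a limited form. In the readable text, no systematic side-effect record is specified before 29 weeks, although drugs can start at about 25-26 weeks. Read literally, the look-back omits the first two weeks of treatment for women who start before about 27 weeks. At starts from 27 weeks to just under 29, coverage depends on the order of contacts; from 29 weeks there is no gap.

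This rests on three assumptions: an OGTT close to 24 weeks for the earliest entrants, a randomization lag of 0-1 week, and visit #3 counting as the last study visit. The share affected is unknown and, on the Abstract's window, probably small. That window is background text and not an entry limit, so it does not remove the gap.

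This is a minor weakness in data collection, worth correcting because the correction is cheap. It affects neither the sample size nor any planned comparison.

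**What to change.** Three wording changes in section VII:

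1. **Additional study visits:** for side-effect recording, replace the 29-to-40-week window with *from the start of drug treatment until delivery*.
2. **Study visit #3:** add the same side-effect question.
3. **Look-back:** at the first contact after drug start, ask about side effects *since starting treatment*; later contacts can keep the existing wording.

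Anchoring on drug start, and not on randomization, avoids extra contacts while a woman is on nutritional therapy alone.

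The cost is one added question at visit #3 and a few extra contacts of up to 10 minutes for early starters. If routine visits before 29 weeks are also 1-2 weeks apart (an assumption), a 25-week start adds about 4/2 = 2 to 4/1 = 4 contacts. If they are less frequent, the question at visit #3 does most of the work. Treatment and sample size are unchanged.
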